### **Outcomes and measures**

Two researchers (Researchers #4 and #5) who are blinded to group allocation will perform all assessments. Participants of both groups will be assessed at baseline (T0), at the end of intervention (T8, 8 weeks after baseline), and at follow-up (T16, 16 weeks after baseline). Table 1 shows the schedule of enrollment, intervention, and assessments according to the SPIRIT guidelines [47].

Table 1 - Schedule of enrollment, intervention, and assessments of the FOCAtrial-II, following SPIRIT guideline

TIMEPOINT	Enrollment	Allocation	Post-allocation	Follow-up	
	T-1	T0	T0	T8	T16
Eligibility screen	X				
Informed consent	X				
Allocation			X		
INTERVENTIONS					
Intervention Group					
Control Group					
ASSESSMENTS					
DPN symptoms		X	X	X	
Fuzzy classification of the DPN severity		X	X	X	
Foot- ankle kinematics and kinetics during gait		X	X	X	
Dynamic plantar pressure distribution during gait		X	X	X	
Tactile sensitivity		X	X	X	
Vibration sensitivity		X	X	X	
Foot health and functionality		X	X	X	
Foot isometric strength		X	X	X	
Functional balance		X	X	X	

An initial anamnesis will be performed to check the eligibility criteria, including clinical, anthropometric, and demographic characteristics of all participants. The classification of DPN severity will be made using the fuzzy score from a web software program [13,53]. Participants with scores equal to or above 2.0, corresponding to mild DPN, will be included in the study. Those who score between 12 and 21 (probable depression) on the Brazilian-Portuguese HADS will not be included [54].

The DPN symptoms and the classification of the DPN severity will be the primary

outcomes. The foot-ankle kinematics and kinetics during gait, plantar pressure distribution during gait, tactile and vibration sensitivities, foot health and functionality, foot strength, and functional balance will be the secondary outcomes.

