## **Aim**

The primary aim of this randomized controlled trial was to investigate the effects of an 8-week home-based physiotherapeutic foot-ankle exercise program using an educational booklet on DPN symptoms and severity. The secondary goal was to investigate the effects of this intervention at 8 and 16 weeks on tactile and vibration sensitivities, foot health and functionality, foot muscle strength, functional balance, plantar pressure, foot-ankle kinematics, and lower limbs kinematics and kinetics during gait.

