## **Methods/Design**

### **Study design and data collection**

This trial is designed as a single-blind, two-parallel arms RCT, wherein patients with DPN will be randomly allocated to either a control group (CG) or an intervention group (IG). This trial protocol follows all recommendations established by SPIRIT (2013) [47], has been approved by a research ethics committee (CAAE: 90331718.4.0000.0065), and was registered at ClinicalTrials.gov on July 2, 2019 (identifier NCT04008745).

Patients in the CG will not receive any specific intervention beyond the usual care, including treatment recommended by the medical team, pharmacological treatment, self-care guidelines, and a weekly telephone call to check on the adherence to care, which will be maintained in both groups [48]. Patients in the IG will perform a foot-related exercise program included in an educational booklet three times/week at home for 8 weeks. After 8 weeks, IG

participants will be encouraged to continue this exercise until the end of the study following the same schedule set in the intervention period. If proven effective, the benefits of the foot-related exercises protocol will be explained and offered to all control participants at the end of the study.

Patients from both groups will be evaluated for all outcomes at baseline (T0), 8 weeks (T8, end of intervention), and 16 weeks (T16, follow-up). All procedures in this study will follow the norms of the Operational Procedure Manual developed specifically for this research. The design and flowchart following the Consolidated Standards of Reporting Trials (CONSORT) guidelines [49] are presented in Fig. 1.

[figure not shown]

Figure 1 - Consolidated Standards of Reporting Trials (CONSORT) flow diagram illustrating the process of FOCA-II.

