### **Fuzzy classification of the DPN severity**

The classification of the DPN severity will be made using the Decision Support System for Classification of Diabetic Polyneuropathy [13,53] developed by the LaBIMPH and publicly available at: <http://www.usp.br/labimph/fuzzy/>. This decision will be based on fuzzy logic with the input variables of signs and symptoms extracted from the MNSI as well as tactile sensitivity (through the number of non-touch areas using a 10-g monofilament) and vibration sensitivity (by vibrating a tuning fork at 128 Hz), characterized as absent, present, or diminished. The software gives a score from 0 to 10, with higher scores indicating more severe DPN.

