Inferential statistical analyses will be conducted using intention-to-treat and per protocol analyses. The missing data will be treated by imputation methods depending on the type: missing completely at random, missing at random, or not at random [65]. The per-protocol analysis will include only those patients who complete follow-up in the allocated intervention group. Confirmation of normality (Kolmogorov–Smirnov test), homoscedasticity (Levene test), and imputation of the means for the missing data of variables with normal distribution will be conducted. After that, mixed general linear models of analysis of variance for repeated measures will be used to detect treatment–time interactions, followed by Newman–Keuls post hoc test to obtain group effect (intervention and control), time effect (between T0, T8, and T16), and group–time interaction. Significant differences will be considered at  $\alpha = 5\%$ , but for the description of the effect of the intervention, the effect size (Cohen coefficient) and difference between the means will be calculated with their respective 95% confidence intervals.

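### Two unranked primary outcomes are each tested at 5% with no control across them; if either one is allowed to carry the trial, the two-sided false-positive rate is about 7% to 9.5%

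*Combined protocol and SAP*

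**What the plan says.** The Aim states one primary objective covering two endpoints: the effect of the "exercise program using an educational booklet on DPN symptoms and severity". Outcomes and measures repeats the pair: "The DPN symptoms and the classification of the DPN severity will be the primary" outcomes. Neither section puts one ahead of the other.

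The Statistical Analysis Plan uses a repeated-measures model to look for treatment-by-time interactions, followed by a Newman-Keuls "post hoc test to obtain group effect (intervention and control), time effect" and the group-by-time interaction. The level is common to all tests ("Significant differences will be considered at" 5%). Two analysis sets are listed ("Inferential statistical analyses will be conducted using intention-to-treat and per protocol analyses") and neither is named as the main one. For description, an effect size and a "difference between the means will be calculated with their respective 95% confidence intervals" are also required.

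The sample size paragraph of the same section uses MNSI, labelled primary, and ankle sagittal range of motion, labelled secondary. The fuzzy score does not enter it.

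**The concern.** With two primary outcomes, the plan has to say what counts as a positive trial, and this one does not. Newman-Keuls compares group and time means within one outcome and does nothing about having two outcomes.

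The gap matters when one outcome is significant and the other is not. The plan as written would then accommodate either a positive or a negative primary conclusion, and the choice could be made with the results in view. If one significant outcome is taken as enough, the nominal 5% does not hold for that claim. The required confidence intervals help a reader judge the size of an effect, but they do not control the error rate of a yes-or-no conclusion.

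**Working it through.** **Reproducing the plan's own sample size.** Inputs from the Statistical Analysis Plan: within-between interaction F-test, 2 groups, m = 2 measurements, alpha 0.05, power 0.80, f = 0.26 (MNSI) and 0.23 (ankle motion). The correlation between repeated measures (rho) is not stated.

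Formula: noncentral F with lambda = f² × N × m / (1 − rho), and degrees of freedom m − 1 and (N − 2)(m − 1).

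- MNSI, rho = 0.5, N = 32: lambda = 0.0676 × 32 × 2 / 0.5 = 8.65; power 81.2%.
- Ankle motion, rho = 0.5, N = 40: lambda = 0.0529 × 40 × 2 / 0.5 = 8.46; power 80.9%.

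These are the smallest even N that reach 80%, so rho = 0.5 reproduces the stated 32 and 40. A rho of 0.3 would give 44 and 54; a rho of 0.7 would give 20 and 26. The target of 40 was therefore set by ankle motion, which leaves MNSI some spare power.

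**False-positive rate across the two primary outcomes.** Take one interaction test per outcome, each at two-sided 5%, with no true effect on either, and test statistics bivariate normal with correlation r:

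- P(either) = 1 − P(|Z1| < 1.96 and |Z2| < 1.96)
- P(both) = 0.05 + 0.05 − P(either)

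| r (assumed) | P(either) | P(both) |
|---|---|---|
| 0 | 9.75% | 0.25% |
| 0.3 | 9.5% | 0.5% |
| 0.5 | 9.1% | 0.9% |
| 0.7 | 8.3% | 1.7% |
| 0.9 | 7.0% | 3.0% |

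At r = 0 this is 1 − 0.95² = 0.0975, the upper bound. If only one outcome has a true effect, a both-required rule can err only through the other outcome's 5% test, so its rate never exceeds 5%.

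The planned analysis has three time points, so the interaction test has 2 numerator degrees of freedom. Simulating that test with 48 patients gave P(either) of 9.75%, 9.3%, 8.4% and 7.1% at r = 0, 0.5, 0.7 and 0.9, in line with the table.

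**What is known about r.** The documents give no value. The section on the fuzzy classification supports a positive one ("This decision will be based on fuzzy logic with the input variables of signs and symptoms extracted from the MNSI"), but tactile and vibration sensitivity are inputs too, so nothing there fixes its size or rules out 0.3.

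**Cost of Holm to MNSI.** In the worst case MNSI is tested at 0.025. Same formula, f = 0.26, m = 2:

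| Evaluable N | rho | lambda | Power at 0.05 | Power at 0.025 |
|---|---|---|---|---|
| 40 | 0.5 | 10.82 | 89.3% | 82.6% |
| 38 | 0.5 | 10.28 | 87.7% | 80.3% |
| 40 | 0.3 | 7.73 | 77.3% | 67.2% |

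The 40 is the plan's evaluable target. The 38 is what remains of 48 after the plan's 20% dropout (48 × 0.8 = 38.4).

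**The case against.** The strongest reply is that the plan never says one outcome is enough. That is correct. A reader might infer that the trial has adopted an either-outcome rule and so has a false-positive rate of 7% to 9.5%. The documents do not support this: the Aim joins symptoms and severity in one objective, which is at least as compatible with requiring both. What stands is that neither reading is excluded.

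A reader might also treat the sentence "If proven effective, the benefits of the foot-related exercises protocol will be explained and offered to all control participants" as a decision rule left undefined. It concerns what control participants are offered after the study. It is not a confirmatory criterion, and the point does not rest on it.

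Third, the sample size paragraph labels MNSI as primary, which might be taken as an implicit ranking. The label separates MNSI from the secondary ankle outcome; it does not place MNSI above the fuzzy score. It does make an MNSI-first order a natural choice.

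Fourth, the 7% to 9.5% counts significance in either direction. Counting only results that favour the exercise program, the chance on at least one outcome is about 3.5% (r = 0.9) to 4.5% (r = 0.5), against 2.5% for a single outcome. This is fair, but the relative inflation is about the same, and the planned F-test rejects for differences in either direction.

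Finally, the outcomes overlap. Overlap reduces the inflation without removing it: 7.0% remains at a correlation of 0.9.

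**Conclusion.** The point holds in conditional form. The plan names two unranked primary outcomes, tests each at 5%, and has no control across them. If significance on either is reported as a positive primary result, the two-sided false-positive rate is about 7% to 9.5%, and at most 9.75%. If both are required, it is at most 5% and no correction is needed.

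The figures assume one interaction test per outcome and correlations of 0.3 to 0.9, which are not taken from the documents. Also treating separate time points, post hoc contrasts or the per-protocol set as routes to success could raise the rate. The inflation is moderate and cheap to prevent, so this should be corrected; it does not invalidate the design.

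**What to change.** Add to the Statistical Analysis Plan, before any outcome data are analysed (before database lock):

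> The two primary tests are the group-by-time interactions for MNSI and for the fuzzy score in the intention-to-treat set. They are controlled at a family-wise 5% by Holm: the smaller p-value is compared with 0.025 and, if significant, the other with 0.05. Per-protocol results and post hoc contrasts are supportive.

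The deadline matters. Under Randomization, allocation, and blinding, the statistician stays blind until the main analysis is complete. A rule added merely before unblinding could therefore be written with both p-values already known, since coded group labels do not hide which outcome is significant.

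Holm needs neither a ranking nor a known correlation, and the plan supplies neither. Its price is the worst-case loss of MNSI power shown in the working: about 7 percentage points at rho = 0.5 and about 10 at rho = 0.3, where power is below 80% even without the correction.

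A fixed order with MNSI first is an acceptable alternative and fits the existing power calculation, which uses MNSI and gives no effect size for the fuzzy score. MNSI loses no power, but the fuzzy score cannot be confirmatory if MNSI is not significant. Requiring both is also valid; its power cannot exceed the lower of the two and cannot be computed without a fuzzy-score effect size.

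Each option takes a few sentences and leaves the planned 48 unchanged.

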### **DPN symptoms**

Patients will answer the Brazilian version of the Michigan Neuropathy Screening Instrument (MNSI) [55]. This questionnaire has 15 questions about the sensitivity of the feet and legs and is self-administered. A score of 1 point is given for answers of “yes” for questions 1, 2, 3, 5, 6, 8, 9, 11, 12, 14, and 15 and “no” for questions 7 and 13. Questions 4 and 10 evaluate circulatory deficits and general asthenia, respectively, and neither are included in the final score. The sum of all scores ranges from 0 to 13, and the larger the score, the worse the DPN.

### **Fuzzy classification of the DPN severity**

The classification of the DPN severity will be made using the Decision Support System for Classification of Diabetic Polyneuropathy [13,53] developed by the LaBIMPH and publicly available at: <http://www.usp.br/labimph/fuzzy/>. This decision will be based on fuzzy logic with the input variables of signs and symptoms extracted from the MNSI as well as tactile sensitivity (through the number of non-touch areas using a 10-g monofilament) and vibration sensitivity (by vibrating a tuning fork at 128 Hz), characterized as absent, present, or diminished. The software gives a score from 0 to 10, with higher scores indicating more severe DPN.

### **Foot-ankle kinematics and kinetics during gait**

Gait kinematics will be assessed by three-dimensional displacements of passive reflective markers (9.5 mm in diameter) tracked by eight infrared cameras at 100 Hz (VERO, Vicon Motion System Ltd., Oxford Metrics, UK) and the NEXUS 2.8 motion capture software (Vicon Motion System Ltd.). Forty-two markers will be placed on both limbs of the subject (pelvis, thigh, leg, ankle, and foot) according to the Plug-In Gait and Oxford Foot Model [56] setup protocols. The laboratory coordinate system will be established at one corner of the force plate, and all initial calculations will be based on it. Each lower-limb segment (shank and thigh) will be modeled based on surface markers as a rigid body with a local coordinate system that coincides with the anatomical axes. Translations and rotations of each segment will be reported relative to the neutral positions defined during the initial static standing trial. All joints will be considered to be spherical (i.e., with three rotational degrees of freedom). Ground reaction forces will be acquired by a force plate (AMTI OR-6-1000, Watertown, MA, USA) embedded in the center of the 10-m walkway at 1 kHz. Force and kinematic data acquisition will be synchronized and sampled by an A/D board (Control Box LOCK VICON, 192 kHz, 24 bits).

Participants will be asked to walk at their comfortable, self-selected speed, with a maximum variation of 5% between measurements, thus ensuring that the same speed is maintained in all assessments (T0, T8, and T16). After a complete habituation to the laboratory environment, 10 valid steps will be acquired on each side during gait.

The automatic digitizing process, 3D reconstruction of the markers' positions, and filtering of kinematic data will be performed using the NEXUS software. Kinematic data will be processed using a zero-lag second-order low-pass filter with cutoff frequency of 6 Hz. Ground reaction force

data will be processed using a zero-lag low-pass Butterworth fourth-order filter with cutoff frequency of 50 Hz.

The bottom-up inverse dynamics method will be used to calculate the ankle moments in the sagittal plane. For the calculation of ankle power, the calculated joint moment and the ankle angular velocity in the sagittal plane will be considered. Calculation of all discrete variables from the time series obtained will be performed using a custom-written MATLAB function (MathWorks, Natick, MA, USA).

The following kinematic variables will be analyzed for the stance phase: (a) sagittal ankle ROM, (b) ankle dorsiflexion at heel strike, (c) ankle plantarflexion at push off, (d) hindfoot to forefoot rotation ROM, (e) transverse plane ROM between first and second metatarsal bones and between second and fifth metatarsal bones, and (f) deformation of the longitudinal medial arch. The ankle kinetic variables to be analyzed are: (a) flexor moment and eccentric power at heel strike and (b) extensor moment and power at approximately 80% of stance phase, corresponding to the propulsion phase.

### **Plantar pressure distribution during gait**

A  $700 \times 403 \times 15.5$ -mm pressure platform (emed q-100, GmbH, Novel, Munich, Germany) with 6080 sensors (four sensors per  $\text{cm}^2$ ) will be used to acquire plantar pressure data during gait at 100 Hz. Participants will walk barefoot three times over the platform with a self-selected gait speed (same as in the kinematic trials), covering a distance of 4 m. Both feet will be analyzed for each patient. Based on the algorithm by Giacomozi [57], peak pressure, contact area, and pressure-time integral in seven anatomical plantar regions—heel, midfoot, medial forefoot,

medium forefoot, lateral forefoot, hallux, and toes—will be analyzed. This method relies on the integration of a 3D motion capture system (Vicon system), a pressure measurement device (emed q-100), a multi-segment foot model, and an algorithm to identify regions of interest.

### **Foot muscle isometric strength**

Foot muscle isometric strength of the flexor muscles of the hallux and lesser toes will be measured according to Mickle [58] using a pressure platform (emed q-100). Subjects will stand and push down on the platform as hard as possible with the toes and hallux, controlling for excessive body sway. The plantar regions corresponding to the hallux and the toes will be identified by a standard mask from Novel-win Multimask software v. 9.35. The average of three trials on each foot (left and right) will be used for statistical purposes. The outcomes will be the maximum force under the hallux and toes, normalized by bodyweight.

### **Tactile sensitivity**

Tactile sensory deficits will be assessed by a 10-g monofilament [48] in four plantar areas (plantar surface of the hallux and heads of the first, third, and fifth metatarsals). This instrument has good reliability and validity in elderly individuals [59]. The monofilament will be applied perpendicularly to the skin surface three times on the tested areas with sufficient force to cause the filament to bend or buckle. The sequence of the tested areas will be randomized. The patient will not be able to see the monofilament or where it is being applied. The number of areas in which the patient does not feel pressure will be recorded [60]. The greater the number of areas marked, the greater the impairment of tactile sensitivity.

### **Vibration sensitivity**

Vibration testing will be conducted with the timed method using a 128-Hz tuning fork applied to the dorsal surface of the distal phalanx of the hallux. The time (in seconds) at which vibration sensation diminishes beyond the examiner's perception will then be recorded from both sides on a standardized form [61]. Values less than 10 s will be classified as present vibratory sensitivity, greater than 10 s will be classified as decreased vibratory sensitivity, and no perception will be classified as absent vibratory sensitivity.

### **Foot health and functionality**

The Brazilian-Portuguese version of the Foot-Health Status Questionnaire (FHSQ-BR), which has been translated and validated by [62], will be used. This questionnaire is divided into three domains, and we will use Domains I and II. These domains are comprised of questions with answer options presented in affirmative sentences and corresponding numbers. Domain I evaluates foot health in four dimensions: foot pain, foot function, footwear, and general foot health. Domain II evaluates the general state of health, also in four dimensions: general health, physical activity, social capacity, and vitality. Domain III collects general demographic data. The domain I and II has a score from 0 to 100 points, where 100 is the best condition and 0 is the worst. The scores will be calculated using the FHSQ software version 1.03 (Care Quest, Australia).

### **Functional balance measure**

The functional balance assessment will be performed according to [63] using the

Functional Reach Test (FRT). Subjects will be asked to assume a standing position without shoes or socks. Patients will be asked to stand with their shoulders perpendicular to the reach measurement device (measuring tape), which will be attached to the wall and parallel to the floor at the height of the patient's acromion. The upper extremity should not contact the wall during the task. In order to maintain identical foot placement during all testing conditions, the foot position will be traced on a sheet attached to the surface of the floor. The initial measurement (Position 1) will correspond to the position where the third metacarpal is in the beginning of the measuring tape and end of the measurement is where the third metacarpal achieve in the measuring tape after the forward movement (Position 2). The patient will then be instructed to lean forward as much as possible without losing balance, flexing the hips, or taking a step. Functional reach will be defined as the mean difference between Positions 1 and 2. Three trials will be performed, and the average score will be used for statistical purposes. The greater the distance achieved, the better the functional balance.

